## Proflavine:

Proflavine powder will be purchased from Sigma-Aldrich and the solution will be prepared by the MD Anderson Investigational Pharmacy Services using specified instructions.

## Data:

The protocol specific data collected will be stored in the Research Electronic Data Capture (REDCap) System/CORe.

Data collected will include the following, as well as all other protocol specific data:

- Age at diagnosis
- Histology
- Date of diagnosis
- Date of surgery
- Operative time
- Duration of time for intraoperative HRME imaging
- HRME imaging findings
- Final pathologic findings

#### 7.0 Potential Side Effects

The HRME imaging system will be used prior to the standard CKC procedure. The standard CKC procedure itself has potential risks including, but not limited to, bleeding, infection and damage to rectum and bladder. These risks will be reviewed with the patient and standard informed consent obtained for the surgical procedure in addition to the study informed consent. There are no known risks associated with the imaging device used in this study.

However, there is the rare possibility of a severe allergic reaction to proflavine, the contrast dye used in imaging. Proflavine may be combustible at high temperatures. Proflavine is the principal component of acriflavine and has been used for fluorescent imaging in the European, Asian, and Australian gastrointestinal literature without any adverse effects noted. Proflavine has been clinically used as an antibacterial agent. In neonatal care, Triple dye, a combination of brilliant green, proflavine hemisulfate, and gentian violet is routinely used as a topical antibacterial agent on the umbilical stump of newborn babies (21), with a recent review of the practice categorizing toxicity as rare (22). We propose the use of proflavine solution at concentrations lower than that of the proflavine component in commercial triple dye, 0.11% (w/v) (Kerr Triple Dye, VistaPharm). We have currently done several patients with Barrett's esophagus under an existing protocol and IND and no complications or adverse events have been reported. The

quantity of solution used for diagnostic imaging is likely to be no greater than that used in neonatal care (0.65 ml per single-use swab). Investigational *in vivo* human studies of confocal microscopy for gastrointestinal cancer currently use topical acriflavine at 0.05% concentration (23).

The additional exposure to light which will occur during imaging can also be compared to that received by newborn babies undergoing phototherapy for jaundice. The high-resolution fiber-optic microendoscope proposed for use here delivers 0.5 mW of 455 nm light to the tissue through a 0.8 mm diameter fiber-optic bundle, corresponding to an irradiance level of 100 mW/cm². The American Academy of Pediatrics defines intensive phototherapy as a spectral irradiance of at least 30 mW/cm² per nanometer over the 430-490 nm spectral band, equivalent to a total irradiance of 1.8 mW/cm² (24). Although the irradiance level is over 50-times higher with the fiber microendoscope system, a typical imaging session of 30 minutes (including imaging for routine care) is approximately 50-times shorter than a typical 24 hour (1440 minutes) phototherapy incubation, leading to an equivalent light dose in each scenario.

The imaging procedure will add approximately 10 minutes to the patient's time in the operating room. There is the rare possibility that there may be additional risks from the added time of additional sedation.

# 8.0 Criteria for Removal from Study:

- 1. Any patient who is consented for the study but prior to surgery declines to participate in the study.
- 2. Any patient in whom the surgery is scheduled but not performed.
- 3. Any patient who withdraws consent for any reason.

## 9.0 Patient Confidentiality

All pathology specimens, evaluations forms, reports and other patient records will be identified in a manner designed to maintain patient confidentiality. All data and specimens will be entered into REDCap/CORe. Clinical information will not be released without the written permission of the patient or the patient's guardian, except as necessary for monitoring by the MD Anderson IND office or its representative, regulatory authorities, or the IRB.

Study data will be collected and managed using REDCap (Research Electronic Data Capture) electronic data capture tools hosted at MD Anderson. [24] REDCap (www.project-redcap.org) is a secure, web-based application with controlled access designed to support data capture for research studies, providing: 1) an intuitive interface for validated data entry; 2) audit trails for tracking data manipulation and export procedures; 3) automated export procedures for seamless downloads to common statistical packages; and 4) procedures for importing data from external sources. In the case of multi-center studies REDCap uses Data Access Groups (DAGs) to ensure that personnel at each institution are blinded to the data from other institutions. REDCap (https://redcap.mdanderson.org) is hosted on a secure server by MD Anderson Cancer Center's Department of Research Information Systems & Technology Services. REDCap has undergone a Governance Risk & Compliance Assessment (05/14/14) by MD Anderson's Information

Security Office and found to be compliant with HIPAA, Texas Administrative Codes 202-203, University of Texas Policy 165, federal regulations outlined in 21CFR Part 11, and UTMDACC Institutional Policy #ADM0335. Those having access to the data file include the study PI and research team personnel. All protected health information (PHI) will be removed from the data when it is exported from REDCap for analysis or review by the study collaborators at Rice University. All dates for a given patient will be shifted by a randomly generated number between 0 and 364, thus preserving the distance between dates. Dates for each patient will be shifted by a different randomly generated number.

The investigators and all employees and co-workers involved with this study shall not disclose or use for any purpose, other than performance of the study, any data, records or other unpublished, confidential information disclosed to those individuals for the purpose of the study. No patient identifiers will be used when analyzing the data or reporting the results.

For this protocol we will only capture adverse events that are determined by the PI to be definitely related to the proflavine and/or HRME imaging. Adverse events and serious adverse events related to the standard of care CKC will not be captured as part of the protocol data

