## 11.0 Serious Adverse Event Reporting (SAE) for MD Anderson-Sponsored IND Protocols

An adverse event or suspected adverse reaction is considered "serious" if, in the view of either the investigator or the sponsor, it results in any of the following outcomes:

- Death
- A life-threatening adverse drug experience any adverse experience that places the
  patient, in the view of the initial reporter, at immediate risk of death from the adverse
  experience as it occurred. It does not include an adverse experience that, had it occurred
  in a more severe form, might have caused death.
- Inpatient hospitalization or prolongation of existing hospitalization
- A persistent or significant incapacity or substantial disruption of the ability to conduct normal life functions.
- A congenital anomaly/birth defect.

Important medical events that may not result in death, be life-threatening, or require hospitalization may be considered a serious adverse drug experience when, based upon appropriate medical judgment, they may jeopardize the patient or subject and may require medical or surgical intervention to prevent one of the outcomes listed in this definition. Examples of such medical events include allergic bronchospasm requiring intensive treatment in an emergency room or at home, blood dyscrasias or convulsions that do not result in inpatient hospitalization, or the development of drug dependency or drug abuse (21 CFR 312.32).

Important medical events as defined above, may also be considered serious adverse events. Any important medical event can and should be reported as an SAE if deemed appropriate by the Principal Investigator or the IND Sponsor, IND Office.

All events occurring during the conduct of a protocol and meeting the definition of a SAE must be reported to the IRB in accordance with the timeframes and procedures outlined in "The University of Texas M. D. Anderson Cancer Center Institutional Review Board Policy for Investigators on Reporting Unanticipated Adverse Events for Drugs and Devices". Unless stated otherwise in the protocol, all SAEs, expected or unexpected, must be reported to the IND Office, regardless of attribution (within 5 working days of knowledge of the event).

All life-threatening or fatal events, that are unexpected, and related to the study drug, must have a written report submitted within 24 hours (next working day) of knowledge of the event to the Safety Project Manager in the IND Office.

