Unless otherwise noted, the electronic SAE application (eSAE) will be utilized for safety reporting to the IND Office and MDACC IRB. Serious adverse events will be captured from the time of the first protocol-specific intervention, until 30 days after the last dose of drug, unless the participant withdraws consent. Serious adverse events must be followed until clinical recovery is complete and laboratory tests have returned to baseline, progression of the event has stabilized, or there has been acceptable resolution of the event.

Additionally, any serious adverse events that occur after the 30 day time period that are related to the study treatment must be reported to the IND Office. This may include the development of a secondary malignancy.

All adverse events encountered during the study will be evaluated according to the NCI Common Toxicity Criteria (CTCAE) version 4.03.

The investigator or physician designee is responsible for verifying and providing source documentation for all adverse events and assigning attribution of all events for subjects enrolled.

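### Section 9.0 captures only adverse events judged definitely related to proflavine or HRME, so possibly and probably related non-serious events stay out of the protocol data; sections 10.0 and 11.0 are not reconciled with this rule

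*Combined protocol and SAP*

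**What the plan says.** **Section 9.0, last paragraph.** Under the Patient Confidentiality heading, the protocol states that "we will only capture adverse events that are determined by the PI to be definitely related to the proflavine and/or HRME imaging". A further sentence deals with harms from the cone itself and leaves them out: "Adverse events and serious adverse events related to the standard of care CKC will not be captured as part of the protocol data".

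**Section 11.0.** The scope here is wider. "Serious adverse events will be captured from the time of the first protocol-specific intervention, until 30 days after the last dose of drug", with no attribution limit in that sentence. On grading, the section is equally broad: "All adverse events encountered during the study will be evaluated according to the NCI Common Toxicity Criteria (CTCAE) version 4.03". For the reporting route, "the electronic SAE application (eSAE) will be utilized for safety reporting to the IND Office and MDACC IRB". Record-keeping falls to the physician in charge or a delegate, who is described as "responsible for verifying and providing source documentation for all adverse events and assigning attribution of all events for subjects enrolled".

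**Section 12.0.** One sentence keeps surgery-related events from being reported or recorded in the case report form.

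**Section 10.0.** Twenty patients are enrolled. Safety is evaluated after the first 5 and after each later cohort of 5. No event set, attribution level, grade or threshold is named for these evaluations.

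**Section 6.0.** The listed data items include no adverse event or attribution item, although a catch-all for other protocol-specific data could cover them. Staff contact each participant within 30 days to ask about symptoms. How the answers are recorded is not stated.

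**The concern.** A rule that admits only definite attributions is demanding in this setting. Acetic acid, proflavine, possibly Lugol's solution with more proflavine, HRME imaging and the cone all take place in one operating-room session, and there is no control group. Section 7.0 names allergic reaction to proflavine and risk from added sedation time as the possible harms. With several exposures close together, either could be hard to call definite (this is an inference from the procedures, not a statement in the protocol).

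Nothing says how to classify an event possibly due to both the agent and the surgery. Such an event fails the definite test and may also be caught by the surgery exclusion.

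What is at stake is the completeness of the non-serious safety data. A report of no events could then reflect the filter as well as the product.

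**Working it through.** **1. The plan's own figure.** The plan gives no safety figure to reproduce. The only computed result in section 10.0 is the 90% credible interval for 18 successes in 20. The posterior is beta(1.8 + 18, 0.2 + 2) = beta(19.8, 2.2), with equal-tailed limits 0.780 and 0.979. This matches the stated 0.78 to 0.98. The present point does not depend on it.

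**2. Where each kind of event goes.** This takes sections 9.0 and 11.0 together on the most workable reading.

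| Event | Graded, sourced, attributed (11.0) | eSAE route (11.0) | Protocol data (9.0) |
|---|---|---|---|
| Non-serious, definitely related | yes | no | yes |
| Non-serious, probably or possibly related | yes | no | **no** |
| Non-serious, possibly due to both agent and surgery | yes | no | **no** |
| Serious, not definitely related | yes | yes | no |

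The second and third rows are the gap. These events exist in source records, but no section brings them into the study data. Serious events have their own route.

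**3. Which data the cohort reviews use.** Section 10.0 speaks of examining data from 5 patients, and section 9.0 says all data go into REDCap/CORe. This suggests that the reviews use the protocol data but does not state it. Source records kept under section 11.0 are not ruled out.

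**4. Illustration of size (assumed inputs only).** Let r be the true per-patient rate of non-serious agent-related events and f the share called definite. With independent patients and at most one event each,

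P(no captured event in n patients) = (1 − r·f)^n.

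Example: r = 0.10, f = 0.5, n = 20 gives (1 − 0.05)^20 = 0.358.

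For n = 20:

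| f | r = 1% | r = 5% | r = 10% | r = 20% |
|---|---|---|---|---|
| 1 (full capture) | 82% | 36% | 12% | 1% |
| 0.9 | 83% | 40% | 15% | 2% |
| 0.75 | 86% | 47% | 21% | 4% |
| 0.5 | 90% | 60% | 36% | 12% |
| 0.25 | 95% | 78% | 60% | 36% |

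For one cohort of 5 at r = 10%, the chance of no captured event is 59% with full capture, 68% at f = 0.75 and 77% at f = 0.5.

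The documents inform neither r nor f. The effect is small if most related events are called definite or if r is near 1%. The formula also ignores error in the other direction, where a cone event is logged as agent-related.

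**The case against.** **Sections 9.0 and 11.0 need not conflict.** A reader might infer a flat contradiction. The text does not force one. Section 9.0 limits its surgery exclusion to the protocol data. In section 11.0 the sentence on capturing serious events directly follows the one naming the eSAE application, so capture there can mean that route. Grading, source documentation and attribution are investigator duties, not rules for database entry. This stands: the passages are unreconciled, not proven contradictory.

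**Serious-event reporting.** A reader might also infer that cone-related serious events would go unreported, against the rule that "All events occurring during the conduct of a protocol and meeting the definition of a SAE must be reported to the IRB". The documents do not establish this. In the section 12.0 sentence, the case report form can govern both verbs, which makes it a rule about that form only. The IND Office rule has its own proviso: "Unless stated otherwise in the protocol, all SAEs, expected or unexpected, must be reported to the IND Office, regardless of attribution". The IRB policy that section 11.0 cites is not in the documents.

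**Harm to the cohort reviews is conditional.** Nothing in section 10.0 bars reviewers from using source records. If they do, the loss is confined to the study data set and whatever is summarised from it. This also stands.

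**The threshold is a sponsor choice.** Safety is not among the objectives in section 1.0. A wider rule would let in events due to the cone, such as the bleeding and infection that section 7.0 lists. That is a real cost, but an attribution field lets such events be separated at analysis. An event never entered cannot be recovered from the data set.

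None of these objections reaches the core. The capture sentence in section 9.0 says only, and followed as written it leaves out possibly and probably related non-serious events.

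**Conclusion.** The point holds in this form. As written, section 9.0 keeps possibly and probably related non-serious events, and events possibly due to both agent and surgery, out of the protocol data. A safety summary drawn from those data would be understated. The cohort-of-5 reviews would be understated too if they rely on the same data, which the protocol leaves open.

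The amount of understatement cannot be derived from the documents. The percentages above are correct arithmetic on assumed rates and should not be read as an estimate. The feasibility and concordance analyses do not use adverse event data. Section 10.0 sets no safety threshold, so no stated decision rule changes. The point should be fixed before the first cohort review, mainly because the correction is cheap.

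**What to change.** 1. **Section 9.0:** replace the definite criterion with capture of every event judged at least possibly related to proflavine and/or HRME, and add an attribution field. Limit the surgery exclusions in sections 9.0 and 12.0 to events judged unrelated to proflavine and HRME, so that events possibly due to both are kept.
2. **Section 10.0:** state that each cohort-of-5 safety review uses this event set.

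If the sponsor keeps the definite criterion for the database, the minimum is one sentence in section 10.0 saying that each review also uses the events source-documented and attributed under section 11.0.

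**Cost:** protocol wording and a slightly longer adverse event log for 20 patients. No extra visit or procedure is needed, since section 11.0 already requires attribution of all events and section 6.0 already provides the symptom contact. The downside is that some logged events will turn out to be due to the cone.

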#### 10.0 Statistical Evaluation

We will enroll 20 patients in this exploratory study. We will first examine data from 5 patients to work out the logistical issues in the use of the imaging technology with the surgery as well as evaluation of safety. We will then examine data from the remaining patients in cohorts of 5. After each cohort of 5 patients we will review the logistics of the imaging technology and make adjustments deemed necessary to improve the surgical procedure. We will also evaluate safety.

Our primary objective is to determine the feasibility of acquiring *in-vivo* high-resolution microendoscopy (HRME) images of cervical adenocarcinoma in-situ (AIS) immediately prior to conization. We will use descriptive statistics to summarize the demographic and clinical characteristics of patients. We will estimate the proportion of patients for whom we can successfully acquire *in-vivo* HRME images of AIS immediately prior to conization with a 90% credible interval, assuming a beta(1.8, 0.2) prior distribution. This prior distribution is based on an anticipated success rate of 90%. If we complete the study with 18 patients for whom we can successfully acquire *in-vivo* HRME images of AIS, then our 90% credible interval will be 0.78 to 0.98. If we are able to successfully acquire in-vivo HRME images of at least 18 of the 20 patients enrolled in the study, then we will determine that the methodology is feasible.

Our secondary objective is to determine the accuracy of HRME images in distinguishing AIS from normal cervical tissue. We will tabulate AIS finding by the CKC specimen results as determined by pathology, and we will estimate the concordance of HRME images taken *ex-vivo* (as described in section 6.0) with pathology findings with a 90% credible, assuming a beta (1.8, 0.2) prior distribution for the concordance.

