# 2.0 Background

# Cervical adenocarcinoma in situ (AIS):

Cervical AIS is a precursor to invasive cervical adenocarcinoma, which accounts for approximately 25% of cervical cancers in the United States (1). While the incidence of squamous cell carcinoma of the cervix has been on the decline in the U.S. due to widespread screening, detection, and treatment of precancerous lesions, the incidence of both AIS and invasive cervical adenocarcinoma has been rising for unclear reasons (2). Similar to squamous cervical intraepithelial neoplasia (CIN) and squamous cell carcinoma, cervical AIS and invasive adenocarcinoma are caused by persistent cervical infections by carcinogenic or high-risk human papillomavirus (HPV). AIS is histologically characterized by atypical columnar epithelial cells with no invasion present. Unlike squamous CIN lesions, 10 to 13% of patients with AIS have multifocal disease, with foci of AIS separated by at least 2 mm of normal mucosa ("skip" lesions) (1,3-5).

The majority of patients are asymptomatic and the diagnosis of AIS is usually made following an abnormal Pap test. There are no clearly distinguishable clinical, cytological or colposcopic features of AIS. The lesion is usually located at the transformation zone with contiguous involvement of the endocervical canal (1,6). Cervical cytology and colposcopy-directed biopsy can miss up to 60% of AIS cases, however, the addition of endocervical curettage (ECC) significantly improves the detection rate (7). Cervical conization is usually required to make the diagnosis of AIS. Cold knife conization is preferred over loop electrosurgical excision procedure (LEEP) as it minimizes the risk of thermal artifact and allows the pathologist to determine the presence of invasive disease and margin status (8-10).

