AlS is difficult to manage conservatively for several reasons. The lesion may be located high in the endocervical canal or be multicentric with "skip" lesions present. The sensitivity of cervical cytology and ECC is therefore only approximately 50%, making it difficult to adequately monitor women with AlS managed conservatively (4,11). In addition, the incidence of residual AlS or invasive adenocarcinoma following conization for AlS is high (3-5, 9, 12-14). Given these challenges, the standard treatment of AlS in women who have completed childbearing is simple hysterectomy. However, if the cervical cone margins are positive, a repeat cervical conization is performed prior to proceeding to simple hysterectomy to confirm negative margins and rule out an invasive occult cancer that could require different treatment. For women who desire future fertility, conservative management with cervical cone is an alternative provided the conization margins and ECC sample are negative. In women with a positive margin or ECC, repeat conization to remove the entire lesion and exclude the presence of invasive disease is recommended.

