# 3.0 Preliminary Data and Rationale

# Cervical adenocarcinoma in-situ (AIS):

Our group recently performed a large, retrospective study evaluating the outcomes of 188 patients with AIS (15). The mean age at diagnosis was 33.8 years (range 17.6-76.1), with many women of childbearing age. One hundred and seventy-two of the 180 women had at least one cone biopsy performed, with 110 (64.0%) undergoing a cold knife cone (CKC), and 62 (36.0%) undergoing a LEEP as their initial method of treatment. Positive margins were noted in 35.0% of patients undergoing CKC compared with 55.6% undergoing LEEP (p=0.017). Seventy-one patients ultimately underwent hysterectomy with residual disease noted in 10 patients (14.1%), 8 patients (11.3%) with residual AIS and 2 patients (2.8%) with invasive carcinoma. Of the 101 patients who did not undergo hysterectomy, 2 patients (2.0%) developed recurrent AIS at a median of 27.5 months (range 18- 37 months) from the last cone, and none developed invasive carcinoma. However, 28.6% of patients required more than one conization to achieve negative margins. The study concluded that conservative, fertility-sparing management of AIS with CKC alone is feasible but that two or more CKCs may be required to obtain negative margins.

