## 4.0 Eligibility Criteria

## Inclusion Criteria:

- 1. Any woman with a confirmed preoperative diagnosis of cervical AIS, including co-existing squamous CIN and/or microinvasive cancer
- 2. Women undergoing cold knife cone (CKC) of the cervix at MD Anderson
- 3. Negative pregnancy test for women of child-bearing potential
- 4. Women who are >/= 21 years of age and < 65 years of age
- 5. Ability to understand and the willingness to provide informed consent and sign a written Informed Consent Document (ICD)

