## **Exclusion Criteria:**

- 1. Women < 21 years of age and >/= 65 years of age
- 2. Women with a known allergy to proflavine or acriflavine
- 3. Women who are pregnant or nursing
- 4. Patients unable or unwilling to provide informed consent or sign a written Informed Consent Document (ICD)

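### The feasibility proportion for images of AIS counts all 20 enrolled women, including any whose study cone contains no AIS, so it mixes presence of disease with HRME performance

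*Combined protocol and SAP*

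**What the plan says.** **Entry.** Section 4.0 admits "Any woman with a confirmed preoperative diagnosis of cervical AIS, including co-existing squamous CIN and/or microinvasive cancer" and "Women undergoing cold knife cone (CKC) of the cervix at MD Anderson". The exclusions cover age, dye allergy, pregnancy or nursing, and consent. Prior conization is not mentioned, and AIS need not be present at the study cone.

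**How women reach a cone.** Section 2.0 says "Cervical conization is usually required to make the diagnosis of AIS". It also says "In women with a positive margin or ECC, repeat conization to remove the entire lesion and exclude the presence of invasive disease is recommended".

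**Primary analysis.** Section 10.0 says "We will estimate the proportion of patients for whom we can successfully acquire" in-vivo images of AIS, with a beta(1.8, 0.2) prior and a 90% credible interval. The worked interval for 18 successes also refers to images of AIS. The next sentence, which sets the go rule at 18 or more of the 20 enrolled, refers only to in-vivo HRME images and leaves out *of AIS*.

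**Handling of AIS-free cones.** Section 8.0 removes women who decline, whose surgery is not performed, or who withdraw consent. No section says how to count a woman whose study cone shows no AIS. Section 6.0 lists final pathology as a data item and does not name prior excision.

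**The concern.** A woman diagnosed by an earlier excision can enrol for a further cone. If no AIS remains, no image of AIS can be obtained however well the probe works, yet she stays in the denominator.

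The two wordings in Section 10.0 then treat her in opposite ways. Under the estimate's wording she is a failure, and feasibility can be missed because disease was absent. Under the go-rule wording she is a success if any image was taken, and she helps to pass a test of whether AIS can be imaged without contributing to it. With 20 patients and a margin of two failures, a few such women can decide the result either way.

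**Working it through.** **1. The plan's own figure.** With 18 of 20 successes the posterior is beta(1.8 + 18, 0.2 + 2) = beta(19.8, 2.2). Its 5% and 95% points are 0.780 and 0.979, matching the stated 0.78 to 0.98. The arithmetic in the plan is sound; the question is what the proportion measures.

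**2. What the proportion measures.** Let q be the chance that AIS is present at the study cone and s the chance that it is imaged when present. On the images-of-AIS wording the success probability is q × s, and only s concerns HRME. The anticipated 90% equals s only if q = 1. With three AIS-free cones at most 20 − 3 = 17 successes are possible, below 18.

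**3. Inputs for an illustration.** The number of repeat cones is not given. Section 3.0 reports that 28.6% of an earlier cohort needed more than one conization, and that 110 of 172 first cones (64.0%) were cold knife.
- One further cone each: 0.286 / 1.286 × 20 = 4.4 repeat cones in 20.
- Counting only cold knife first cones, with all repeats cold knife: 0.286 / (0.640 + 0.286) × 20 = 6.2.

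So 4 and 6 are used as assumptions. The share r of repeat cones that still contain AIS is also assumed, at 50% to 80%. First-excision patients are all taken to have AIS.

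**4. Chance of 18 or more of 20 with an image of AIS.** For k repeat cones, successes are Binomial(20 − k, s) + Binomial(k, r × s). With k = 6 and s = 1, at least 4 of the 6 must contain AIS:
- r = 0.50: (15 + 6 + 1) / 64 = 0.344
- r = 0.80: 0.246 + 0.393 + 0.262 = 0.901

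| Repeat cones | r | s = 1.00 | s = 0.90 |
|---|---|---|---|
| 0 | – | 1.00 | 0.68 |
| 4 | 0.50 | 0.69 | 0.20 |
| 4 | 0.80 | 0.97 | 0.47 |
| 6 | 0.50 | 0.34 | 0.09 |
| 6 | 0.70 | 0.74 | 0.26 |
| 6 | 0.80 | 0.90 | 0.38 |

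**5. Effect of the denominator.** Suppose 15 of 20 cones contain AIS and all 15 are imaged. Over 20 the 90% interval is 0.605 to 0.895 and the rule fails. Over the 15 with AIS it is 0.939 to 1.000.

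**6. Carrying the threshold to a smaller denominator.** The posterior mean is (1.8 + x) / (2 + n). It is at least 0.90 exactly when x ≥ 0.9n, which gives 18 at n = 20. At n = 17, 0.9 × 17 = 15.3, so 16 are needed (94.1%). That is the same count as scaling 18 of 20 and rounding up. At a true rate of 90%:

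| n | Needed for posterior mean ≥ 0.90 | Chance of passing |
|---|---|---|
| 20 | 18 | 0.68 |
| 18 | 17 | 0.45 |
| 17 | 16 | 0.48 |
| 15 | 14 | 0.55 |
| 14 | 13 | 0.58 |

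A looser rule of 15 of 17 passes with chance 0.76 and has posterior mean 16.8 / 19 = 0.884.

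**The case against.** The strongest reply is that women sent for repeat conization are selected for likely disease. Section 2.0 ties the repeat cone to a positive margin or ECC, so many would still have AIS. Some women will also have been diagnosed by biopsy or ECC: Section 2.0 says cytology and directed biopsy miss up to 60%, and that ECC improves detection. This stands, and it is why the illustration uses 50% to 80%. It lowers the expected number of AIS-free cones but does not supply a rule for them.

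A reader might infer that women whose AIS has already been removed do enter in number, and that the proportion therefore reflects residual disease and not HRME. The documents do not support this. They show that such women can enter, not that they do, and the proportion is a product in which HRME performance remains a factor.

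A reader might also apply the 14.1% residual disease at hysterectomy from Section 3.0. With 6 repeat cones and perfect imaging, a 14% rate would give a pass chance of 0.005. That figure describes a different group: Section 2.0 places re-conization to confirm negative margins before hysterectomy. It also includes 2 invasive cases; residual AIS alone was 8 of 71 (11.3%).

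On the go-rule wording, residual disease cannot cause failure. That is true, but the rule then does not test the stated primary objective.

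Two smaller replies also stand. The Section 6.0 data list is not exhaustive. AIS-free cones still supply normal sites for the accuracy objective.

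**Conclusion.** The point holds as a gap in the definition of the primary result. Eligibility permits AIS-free study cones, no rule covers them, and the two wordings in Section 10.0 count them in opposite ways. The unreachability of 18 of 20 with three or more such cones is exact on the images-of-AIS wording.

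The size is illustrative. With 6 repeat cones, of which 50% to 80% contain AIS, the pass chance at the plan's 90% imaging rate falls from 0.68 to between 0.09 and 0.38. With perfect imaging it falls from 1.00 to between 0.34 and 0.90. The repeat-cone count and the residual rate are both assumptions. If nearly all study cones contain AIS, the effect is small. The matter is worth settling before enrolment because the repair is cheap; it does not invalidate the design.

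**What to change.** In Section 10.0:

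1. Reconcile the two wordings and define success for a patient, including what makes an in-vivo image one *of AIS*. Section 6.0 places the co-registration ink dots on the removed specimen only, so this link is not yet stated.
2. Apply the 18 of 20 rule to technical in-vivo image acquisition in all 20 enrolled.
3. Estimate in-vivo imaging of AIS among patients whose final CKC pathology shows AIS, with the same beta(1.8, 0.2) prior and 90% credible interval.
4. Judge that estimate by a criterion fixed in advance and tabulated for each possible denominator with its chance of passing. A posterior mean of at least 0.90 is one candidate and agrees with 18 of 20 when n = 20. As shown above, it requires 16 of 17, which is stricter than the current rule, so that cost should be accepted openly or a looser criterion chosen.
5. Add prior excision (none, LEEP, CKC) to the Section 6.0 data list and show both results by it.

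The cost is wording and one chart-review field. Final pathology is already collected, and no extra patients or change in eligibility are needed. The downside is a smaller denominator for the AIS-specific estimate and, at the same observed proportion, a wider interval.
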